I have read this protocol. I approve this document and I agree that it contains all necessary details for carrying out the study as described. I will conduct this study in accordance with the design and specific provision of this protocol and will make a reasonable effort to complete the study within the time designated. I will provide copies of this protocol and access to all information furnished by Matinas BioPharma Nanotechnologies, Inc. to study personnel under my supervision. I will discuss this material with them to ensure they are fully informed about the study product and study procedures. I will let them know that this information is confidential and proprietary to Matinas BioPharma Nanotechnologies, Inc. and that it may not be further disclosed to third parties. I understand that the study may be terminated or enrollment suspended at any time by Matinas BioPharma Nanotechnologies, Inc., with or without cause, or by me if it becomes necessary to protect the best interests of the study subjects.

I agree to conduct this study in full accordance with Food and Drug Administration Regulations, Institutional Review Board/Ethic Committee Regulations and ICH Guidelines for Good Clinical Practices.

Investigator's Signature

Date

Investigator's Printed Name

SYNOPSIS

TITLE: A Multi-Center Randomized Study to Evaluate the Safety, Tolerability, and Efficacy of Oral Encocleated Amphotericin B (CAMB) Compared With Oral Fluconazole in the Treatment of Moderate to Severe Vulvovaginal Candidiasis

PROTOCOL NUMBER: MB-70005

INVESTIGATIONAL PRODUCT: MAT2203 encochleated amphotericin B (CAMB)

PHASE: 2

INDICATION: Moderate to severe vulvovaginal candidiasis

OBJECTIVES:

The primary objective of this study is to evaluate the safety of 200 mg (100 mg twice daily [BID]) and 400 mg (200 mg BID) doses of oral CAMB for 5 days compared with a single 150 mg dose of oral fluconazole in subjects with moderate to severe vulvovaginal candidiasis (VVC).

The secondary efficacy objectives of this study are the following:

- Assess the clinical cure rate of oral CAMB compared with oral fluconazole at the Test-of-Cure (TOC) Visit (Day 12);
- Assess the mycology eradication rate for oral CAMB compared with oral fluconazole at the TOC Visit (Day 12); and
- Assess the responder outcome by treatment group, separately, at the TOC Visit (Day 12).

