The Modified Intent-to-Treat (mITT) Population will include all randomized subjects who have a *Candida* species isolated on culture of vaginal specimen at baseline based on the central laboratory results.

The Safety Population will include all ITT subjects who received at least 1 dose of study drug.

The PK Population will include the subjects in the ITT Population with at least 1 PK sample.

The Per-Protocol Population will include all of the mITT subjects who meet the following criteria:

- No key inclusion/exclusion violations;
- Received the complete course of study drug;
- No major protocol violations that would affect the treatment evaluation; and
- Has not received another systemic or topical antifungal drug that has documented activity against the causative organism before the TOC assessment, unless the subject has a therapeutic response of failure at a previous assessment visit.

EFFICACY VARIABLES:

The efficacy endpoints for this study will be performed on the mITT Population and Per-Protocol Population and will include the following:

1. The proportion of subjects with clinical cure at the TOC Visit (Day 12);
2. The proportion of subjects with mycological eradication at the TOC Visit (Day 12); and
3. The proportion of subjects with overall success at the TOC Visit (Day 12).

For the definition of clinical cure, mycological eradication, and overall success, see below.

Assessment of Clinical Outcome

Clinical outcomes will be assessed at the TOC Visit (Day 12) according to the following definitions:

- Clinical cure – resolution of the VVC signs and symptoms that were present at baseline without further antifungal treatment. Specifically, any sign or symptom with a score of 1 or 2 at entry should be absent (score = 0) by the TOC Visit. Any sign or symptom with a score of 3 (severe) at entry should have a score of 0 or 1 by the TOC Visit. If a new sign or symptom is observed at the TOC Visit that was not present at entry, the Investigator should state whether the new sign or symptom is related to VVC or not (ie, if related, the subject would be considered a failure; if not related, the subject may be considered a cure);
- Clinical failure – incomplete resolution of signs and symptoms of VVC that were present at baseline or new signs and symptoms have developed and require the initiation of non-study antifungal drugs; and
- Clinical indeterminate – insufficient data are available to determine if the subject is a cure or failure.

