Assessment of Mycological Outcome

Mycological outcomes will be assessed at Day 12 (± 2 days) (TOC Visit) according to the following definitions:

- Mycological eradication – a vaginal swab culture negative for growth of baseline *Candida* species;
- Mycological persistence – a vaginal swab culture positive for growth of baseline *Candida* species; and
- Mycological indeterminate – no vaginal swab culture is available, or the culture cannot be interpreted for any reason, or the culture is considered contaminated.

Assessment of Overall Response

Overall response will be assessed at Day 12 (± 2 days) (TOC Visit) according to the following definitions:

- Overall success – achievement of both a clinical cure AND microbiologic eradication;
- Overall failure – clinical failure OR microbiological persistence; and
- Overall indeterminate – insufficient data are available to determine if the subject is an overall success or failure.

The assessment of overall response at the TOC Visit is summarized below.

Summary of Overall Response at the Test-of-Cure Visit

Clinical Outcome	Mycological Outcome		
	Eradication	Persistence	Indeterminate
Cure	Success	Failure	Indeterminate
Failure	Failure	Failure	Failure
Indeterminate	Indeterminate	Failure	Indeterminate

SAFETY VARIABLES:

Safety assessments will include clinical laboratory assessments (including serum chemistry, hematology, and urinalysis), vital signs, body weight, ECGs, both complete and symptom-based physical examinations, prior and concomitant medication reporting, and adverse event reporting.

Hepatotoxicity

Hepatotoxicity will be defined as post-baseline aminotransferase $\geq 3 \times$ ULN.

Nephrotoxicity

Nephrotoxicity will be defined as a 50% increase in serum creatinine from baseline or an increase by ≥ 0.3 mg/dL.

Hypokalemia

Hypokalemia will be defined as serum potassium ≤ 2.5 mmol/L.

PHARMACOKINETIC PARAMETERS:

The PK parameters will include the following:

- AUC: area under the concentration-time curve,
- CL: clearance,
- C_{\max} : maximum plasma concentration,
- C_{trough} : concentration of pre-dose CAMB,
- $t_{1/2}$: terminal elimination half-life, and
- T_{\max} : time to maximum plasma concentration.

STATISTICAL ANALYSES:

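### Mycological eradication counts a negative Day 12 culture even when another active antifungal was given before the swab, although clinical cure does not allow this

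*Combined protocol and SAP*

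**What the plan says.** All references are to the synopsis of the combined protocol and SAP.

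- **Objectives.** One secondary objective is to compare the mycology eradication rate between CAMB and fluconazole at TOC.
- **Assessment of Mycological Outcome.** Eradication is "a vaginal swab culture negative for growth of baseline" *Candida* species. Persistence is the positive counterpart. Indeterminate covers a culture that is missing, contaminated or not interpretable. None of the three mentions other antifungal treatment.
- **Assessment of Clinical Outcome.** Cure is "resolution of the VVC signs and symptoms that were present at baseline without further antifungal treatment". Failure is incomplete resolution of the baseline signs and symptoms, or that "new signs and symptoms have developed and require the initiation of non-study antifungal drugs".
- **Analysis Populations.** The mITT requires randomisation and a baseline central-laboratory culture positive for *Candida*, and nothing about later treatment. The Per-Protocol Population requires among other things "Received the complete course of study drug" and "Has not received another systemic or topical antifungal drug that has documented activity against the causative organism before the TOC assessment", the latter "unless the subject has a therapeutic response of failure at a previous assessment visit".
- **Statistical Analyses.** Clinical cure, mycological eradication and overall success are each reported as a percentage by treatment group, in both populations and descriptively.

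**The concern.** The objective is to learn how often each randomised drug clears the organism. A culture that turns negative after a different active antifungal does not answer that, yet the definition scores it as eradication for the randomised arm. The plan has already decided the matter the other way for clinical cure, so two efficacy endpoints in the same table would treat the same woman differently.

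The situation is not remote. The clinical failure definition and the fourth Per-Protocol criterion both foresee non-study antifungals. The Visit Schedule also tells women to contact the investigator for re-assessment if symptoms have not improved within 2 to 3 days, well before Day 12.

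What is at stake is the meaning of one of three efficacy percentages. Efficacy is reported only descriptively in this proof-of-concept study, so those percentages are its efficacy result.

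**Working it through.** **Step 1. The plan's own figure.** Sample Size Determination gives about 75 mITT subjects at 75% evaluable: 75/0.75 = 100 randomised, as stated. With 1:1:1 allocation, 75/3 = 25 mITT women per arm. The plan gives no alpha, power or effect size, so there is no power calculation to reproduce.

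**Step 2. One woman followed through the definitions.** Take a woman with a positive baseline culture who receives another active antifungal before the TOC swab, and whose signs have resolved and whose culture is negative at TOC.

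| Item | Rule applied | Result |
|---|---|---|
| mITT membership | Baseline culture only | Included |
| Mycological outcome | Culture negative for the baseline species | Eradication |
| Clinical outcome | Further antifungal given | Not a cure |
| Overall response | Success needs clinical cure | Not a success |
| Per-Protocol membership | Other active antifungal before TOC | Excluded, unless the earlier-failure exception applies and the course was complete |

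Three observations follow.

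- The mITT eradication count includes her. The Per-Protocol count can include her through the exception.
- Her clinical category is open. She is not a cure, but she does not plainly meet either limb of failure, and her data are not insufficient. The overall-response table therefore has no clear row for her.
- A woman swabbed before the other drug was started is correctly scored and is not part of this point.

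**Step 3. Size in the mITT.** Reclassifying one woman changes the numerator by 1 and leaves the denominator at 25: 1/25 = 4.0 percentage points. As an illustration with assumed counts, if 15 of 25 women are eradicated without other treatment (60%) and 3 more are culture-negative after another antifungal, the rate as written is 18/25 = 72%. Counting those 3 as non-successes returns it to 60%.

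**Step 4. Effect on a between-arm difference.** The shift is 4 × (count in the CAMB arm − count in the fluconazole arm) points. The documents give neither count. For scale, the 95% half-width of a difference at 25 per arm is 1.96 × √(2p(1 − p)/25), with p assumed equal in both arms:

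| p (assumed) | Half-width, points |
|---|---|
| 0.5 | 27.7 |
| 0.6 | 27.2 |
| 0.7 | 25.4 |
| 0.8 | 22.2 |

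A net excess of 6 women (22.2/4 = 5.5) to 7 women (27.7/4 = 6.9) in one arm would be needed to exceed this. With 0 to 3 such women per arm (assumed), the largest shift is 3 × 4 = 12 points, inside the half-width.

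**Step 5. Size in the Per-Protocol Population.** If it holds 15 to 25 women per arm (assumed), each woman kept by the exception moves her arm's rate by 1/25 = 4.0 to 1/15 = 6.7 points. How many would be kept cannot be worked out. The exception depends on failure at an earlier visit, while the synopsis states that "Clinical outcomes will be assessed at the TOC Visit (Day 12) according to the following definitions" and defines no earlier failure.

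**The case against.** The strongest reply is that eradication is a laboratory outcome, and that reporting the culture whatever else was given is a recognised choice. Attribution is already protected in clinical cure and overall success, and the Per-Protocol rule removes most affected women from the third endpoint. The study is a proof of concept with safety as its primary objective, efficacy is descriptive, and no test or decision changes. All of this is right about consequence and keeps the point modest. It does not settle the mITT eradication rate, where the plan departs from its own rule for clinical cure without giving a reason. Reporting the raw culture is still worthwhile, as a sensitivity analysis.

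Two replies bear on how many women are affected. The TOC visit doubles as the early-withdrawal visit, so some women may be swabbed before switching. The phrase about uninterpretable cultures might also be stretched to cover these swabs. The first may reduce the number, but the synopsis does not require that order. The second would leave a technically valid culture to case-by-case judgment.

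A further reply is that only the synopsis was supplied, and handling rules are often abbreviated there. That stands: a rule elsewhere in the plan would answer the point.

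Three stronger readings are tempting and are not supported.

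- **That the comparison is biased towards one drug.** Neither the counts nor the direction can be derived.
- **That fluconazole gains in the Per-Protocol analysis because its course is complete on Day 1.** The complete-course criterion can remove a woman who stops CAMB early to switch, and cannot do so for fluconazole. But a fluconazole woman is kept only after a failure at an earlier assessment, and no post-baseline assessment falls on Day 1. The unscheduled re-assessment visits might also count as earlier visits. No difference between arms can be calculated from this.
- **That the Per-Protocol exception should be redefined.** Tying it to the scheduled Day 5 assessment would drop women recognised as failing before then and could raise the Per-Protocol cure rates.

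**Conclusion.** The point holds as a defect in an endpoint definition and should be fixed. Followed as written, the synopsis scores a woman swabbed after another active antifungal as eradicated in her randomised arm. This applies in the mITT and, where the exception applies, in the Per-Protocol Population.

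The size is 4.0 points per woman in the mITT, assuming the planned 75 subjects split evenly across three arms. The case rests on what the endpoint measures, not on a demonstrated bias: plausible small counts stay within sampling error. Confidence is medium, because the rest of the plan could not be checked.

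**What to change.** 1. For the eradication endpoint in both populations, count as a mycological non-success any subject who received a non-study antifungal with documented activity against her baseline organism, for any reason, before the TOC swab. Keep her in the denominator and show her in a category of her own, not as culture-positive persistence. Limiting the rule to drugs given for VVC would leave part of the gap open; neither clinical cure nor the Per-Protocol rule has that limit.
2. For analysis, classify a woman whose signs resolved after such treatment as a clinical failure (non-cure). Every cell of the failure row in the existing overall-response table is a failure, so she needs no new column. The team should also state which row applies if her TOC scores are missing.
3. Report the raw culture result as a sensitivity analysis, with the number of such women in each arm.

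The cost is edits to the mycological and clinical outcome definitions and one extra summary. Concomitant medications and TOC cultures are already collected, and patient care does not change. The downside is that eradication rates will be slightly lower, and a woman whom the study drug would have cleared anyway counts as a non-success. The sensitivity analysis shows the most that this can amount to.

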6. Has other urogenital infection(s) that would potentially alter their response to disease;
7. Has confirmed or suspected *N. gonorrhoea* or *C. trachomatis*;
8. Has another vaginal or vulvar condition that would confound the interpretation of clinical response;
9. Has a physiological or pathological condition that would confound the interpretation of clinical response (eg, cervicitis, aerobic vaginitis, atrophic vaginitis, and mucoid ectopy);
10. Has any of the following laboratory abnormalities at screening:
 - a. Alanine aminotransferase (ALT), or aspartate aminotransferase, or alkaline phosphatase levels $>5 \times$ upper limit of normal (ULN);
 - b. Total bilirubin level $>2.5 \times$ ULN;
 - c. Estimated creatinine clearance <70 mL/min;
 - d. Absolute neutrophil count less than 500 cells/ μ L; or
 - e. Potassium level ≤ 3.5 mmol/L;
11. Plans to undergo treatment or surgery for cervical intraepithelial neoplasia or cervical carcinoma during the study period;
12. Has any known azole-resistant *Candida* infection;
13. Has documented Type I diabetes mellitus, use of insulin, or glycosylated hemoglobin A_{1c} level $>10\%$ within 6 months of enrollment;
14. Has previously diagnosed human immunodeficiency virus seropositivity or clinically diagnosed acquired immunodeficiency syndrome or its related complex;
15. Has a known immunosuppressive condition (eg, end-stage renal disease) or is currently taking immunosuppressants, (eg, steroids, cyclosporine);
16. Is currently receiving therapy with a drug known to prolong QTc interval that is metabolized via the cytochrome P450 3A4 enzyme, such as cisapride, astemizole, pimozide, and quinidine;
17. Has been exposed to any investigational agent during the last month (30 days or 5 half-lives, whichever is longer) prior to screening; or
18. Has any other condition the Investigator believes would interfere with the subject's ability to provide informed consent, comply with study instructions, or puts the subject at undue risk.

DOSAGE FORMS AND ROUTE OF ADMINISTRATION:

Encocleated amphotericin B will be administered as a 5 mg/mL oral suspension of 200 mg (100 mg [20 mL] BID) or 400 mg (200 mg [40 mL] BID) amphotericin B on Days 1 through 5.

Fluconazole will be administered once as a single 150 mg tablet on Day 1.

ANALYSIS POPULATIONS:

The Intent-to-Treat Population (ITT) will include all subjects who were randomized.

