Summary statistics will be presented by treatment group. For continuous variables, the number of observations (n), mean, standard deviation, median, minimum, and maximum will be provided. For categorical variables, the frequency and percentage in each category will be displayed.

Efficacy analyses will be performed on the mITT and Per-Protocol Populations. The percentage of subjects with clinical cure, mycological eradication, and overall success will be summarized descriptively by treatment group. Clinical outcome, mycological outcome, and overall response will also be tabulated by treatment group.

Safety analyses will be performed on all subjects in the Safety Population. Analyses will be based on adverse events, vital signs, clinical laboratory assessments, physical examination findings, and ECGs. Safety analyses in general will be descriptive and will be presented in tabular format with the appropriate summary statistics.

The proportion subjects with hepatotoxicity, nephrotoxicity, and hypokalemia will be summarized by treatment group

Descriptive statistics will be provided for PK concentration data and PK parameters. All PK analyses will be performed using the PK Population.

SAMPLE SIZE DETERMINATION:

Approximately 75 subjects are planned for the mITT population. Assuming 75% of randomized subjects will be evaluable for the mITT Population, a total of approximately 100 subjects will be randomized. The sample size was determined empirically rather than with a specific statistical rationale and is considered sufficient to achieve the study objectives. No formal sample size calculations were made.

SITES: Approximately 20 sites in the United States.

SPONSOR:

Matinas BioPharma Nanotechnologies, Inc.
[name]
[name]
United States of America
[contact]

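### Hepatotoxicity is any post-baseline aminotransferase of 3×ULN or more, yet entry is allowed up to 5×ULN, so a subject can be counted without any rise

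*Combined protocol and SAP*

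**What the plan says.** All references are to the Synopsis of the combined protocol and SAP.

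- **Event definition (Safety Variables, Hepatotoxicity):** "Hepatotoxicity will be defined as post-baseline aminotransferase" at or above 3×ULN. There is no further condition.
- **Entry limit (Exclusion Criteria, 10a):** "Alanine aminotransferase (ALT), or aspartate aminotransferase, or alkaline phosphatase levels" exclude a subject only when above 5×ULN at screening.
- **Nephrotoxicity (Safety Variables):** "Nephrotoxicity will be defined as a 50% increase in serum creatinine from baseline", or a rise of at least 0.3 mg/dL.
- **Hypokalemia (Safety Variables):** "Hypokalemia will be defined as serum potassium ≤ 2.5 mmol/L". Exclusion criterion 10e bars entry at "Potassium level ≤ 3.5 mmol/L".
- **Reporting (Statistical Analyses):** "The proportion subjects with hepatotoxicity, nephrotoxicity, and hypokalemia will be summarized by treatment group". The analysis set is given by "Safety analyses will be performed on all subjects in the Safety Population", which means every randomized subject who took at least one dose. The approach is set out as "Safety analyses in general will be descriptive and will be presented in tabular format with the appropriate summary statistics".

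**The concern.** The event definition is an absolute threshold that lies inside the range allowed at entry. The term post-baseline fixes when the sample is taken; it does not require the value to have risen or the baseline to have been lower. A subject who enters at 4×ULN and stays at 4×ULN, or falls to 3×ULN, therefore appears in the table as a case of hepatotoxicity on her assigned drug.

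The trial's primary objective is the safety of the two CAMB doses compared with fluconazole, and this is one of only three toxicity proportions the plan names. In arms of about 33, a single subject whose enzymes did not worsen can create a visible difference between arms, or hide one. The proportion as defined gives the reader no means of seeing that she did not worsen.

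**Working it through.** **Step 1. Can the rule be met without a rise?** Eligibility requires screening ALT and AST of no more than 5×ULN; the event requires a post-baseline value of at least 3×ULN. Pairs of values in multiples of ULN:

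| Baseline → post-baseline | Eligible | Counted | Rise |
|---|---|---|---|
| 3 → 3 | yes | yes | no |
| 4 → 4 | yes | yes | no |
| 4.8 → 3.2 | yes | yes | no |
| 5 → 3 | yes | yes | no |
| 5 → 5 | yes | yes | no |
| 4 → 2.9 | yes | no | no |
| 1 → 3 | yes | yes | yes |

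Five of the seven pairs are counted with no rise. A fall from 4 to 3 is (4 − 3)/4 = 25%. The largest fall that still counts is (5 − 3)/5 = 40%.

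**Step 2. Do the other two toxicities share the problem?** Entry requires potassium above 3.5 mmol/L and the event requires 2.5 mmol/L or less, so a fall of more than 3.5 − 2.5 = 1.0 mmol/L is needed. Nephrotoxicity is defined by an increase in creatinine. Neither can be met by an unchanged eligible value.

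**Step 3. Size per subject.** The plan's own total reproduces: 75 mITT subjects at 75% evaluable gives 75/0.75 = 100 randomized. At 1:1:1 this is 100/3, or about 33 per arm. One subject is 1/33 = 3.0 percentage points.

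**Step 4. How likely is it to matter?** The documents give no frequency for entry at 3 to 5×ULN, so the prevalence q below is an assumption and the results are illustrative. Arms are treated as independent Binomial(33, q), and all such subjects are taken to stay at or above 3×ULN.

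- At least one in a given arm: 1 − (1 − q)^33.
- A given CAMB arm and fluconazole have different counts: 1 − Σ pmf(k)².
- Excess against that CAMB arm: half of that, by symmetry.
- None in the trial: (1 − q)^99.

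| Assumed q | 0.1% | 0.5% | 1% | 2% |
|---|---|---|---|---|
| Expected per arm (33q) | 0.033 | 0.165 | 0.33 | 0.66 |
| At least one in a given arm | 3% | 15% | 28% | 49% |
| Counts differ, either direction | 6% | 26% | 43% | 60% |
| Excess against that CAMB arm | 3% | 13% | 21% | 30% |
| None in the whole trial | 91% | 61% | 37% | 14% |

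If only half of them stay at or above 3×ULN, q is replaced by q/2:

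| Assumed q | 0.1% | 0.5% | 1% | 2% |
|---|---|---|---|---|
| At least one in a given arm | 2% | 8% | 15% | 28% |
| Counts differ, either direction | 3% | 15% | 26% | 43% |
| Excess against that CAMB arm | 2% | 7% | 13% | 21% |

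**The case against.** The logic and arithmetic are hard to dispute; the serious case on the other side is about weight.

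- **No decision rests on this proportion.** The trial is a proof-of-concept study, safety is summarized descriptively, and the available text attaches no test, margin or stopping rule to the figure. This stands, and it limits the consequence to a misleading table entry.
- **Randomization balances baseline status.** It does so in expectation, but one subject in arms of about 33 cannot be split between them.
- **The prevalence range is assumed.** This stands. Nothing in the documents favours any value in it, and at the low end the problem will most likely not arise. Exclusion criterion 18 (investigator judgement) could lower the number further, though it sets no laboratory limit. The only size that follows from the documents is 3 points per subject.
- **Other liver data will exist.** Laboratory summaries by group are planned and screening values are recorded, so a counted subject's entry value could be looked up. That helps a careful reader but does not correct the labelled proportion, and explaining a case away after the data are seen is weaker than a rule fixed beforehand.
- **Only the synopsis is available.** A fuller laboratory section might contain shift tables or a baseline condition. This cannot be checked; the finding is that the available text contains neither.
- **An absolute count is coherent and conservative.** It is, and it is worth keeping. It becomes misleading when reported as toxicity without reference to entry values that the protocol itself allows.

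**Conclusion.** The concern holds. Followed as written, the plan labels an eligible subject who is stable or improving within 3 to 5×ULN as a case of hepatotoxicity, and it is the only one of the three named toxicities that can be met with no change. That conclusion needs no assumption beyond the two stated thresholds.

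The practical effect is modest and its likelihood unknown, since it depends on how many women enter in that range and how many remain there. The point should be fixed because the measure serves the primary objective and the remedy is small. It does not threaten the trial's validity.

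**What to change.** Keep the stated count of all Safety Population subjects with a post-baseline aminotransferase of at least 3×ULN, and add a sentence splitting it by the last value before the first dose (the screening value, if that is the only pre-dose chemistry):

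- **(a) ALT and AST both below 3×ULN at baseline:** report as treatment-emergent hepatotoxicity, with these subjects as the denominator.
- **(b) ALT or AST at or above 3×ULN at baseline:** for each enzyme, report the worst post-baseline value divided by the subject's own baseline. Stable or improving subjects are then not labelled as toxicity, and a true rise remains visible.

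Base the comparison between groups on (a), read together with (b). No cut-off is set for the ratio in (b), because choosing one would be a clinical decision. The 3×ULN threshold, eligibility and subject care are unchanged.

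The cost is one sentence in the definition and one or two table rows, from laboratory values already collected. The drawback is that two rows must be read together instead of one, and (b) may be empty or hold only one or two subjects.

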The tertiary objective of this study is to assess optional pharmacokinetics (PK) (ie, area under the concentration-time curve [AUC], clearance [CL], maximum plasma concentration [C_{max}], terminal elimination half-life [$t_{1/2}$], and time to maximum plasma concentration [T_{max}]) of CAMB after 5 days of oral administration.

POPULATION:

The population for this study will be women age 18 to 65 years, inclusive, with a clinical diagnosis of moderate to severe VVC.

STUDY DESIGN AND DURATION:

This is a proof-of-concept, multi-center, randomized study to evaluate the safety, tolerability, and efficacy of 200 mg (100 mg BID) CAMB and 400 mg (200 mg BID) CAMB compared with a single 150 mg dose of fluconazole in the treatment of moderate to severe VVC.

Approximately 100 women with moderate to severe VVC will be randomized in a 1:1:1 ratio to 1 of 3 treatment groups (200 mg CAMB, 400 mg CAMB, or fluconazole). Randomization will be stratified by a signs and symptoms composite score of up to 12 (moderate) and ≥ 13 (severe).

Scoring of Symptoms and Signs of Vulvovaginal Candidiasis

Vulvovaginal candidiasis signs and symptoms will be evaluated at screening and Days 1, 5, and 12. Signs of VVC will be defined as the presence of erythema, edema, or excoriation. Symptoms of VVC will be defined as itching, burning, or irritation.

Each vulvovaginal sign and symptom will be objectively scored based on severity as follows:

- 0 = none (complete absence of any signs or symptoms),
- 1 = mild (slight),
- 2 = moderate (definitely present), or
- 3 = severe (marked, intense).

Dosing Schedule

For subjects randomized to 200 mg CAMB and 400 mg CAMB, the preferred dosing regimen on Days 1 through 4 is 100 mg BID and 200 mg BID, respectively, with morning and evening meals. On Day 1, subjects will be administered the first dose according to their treatment assignment with a non-standardized meal or snack in the clinic.

On Day 1, subjects randomized to 200 mg CAMB who enroll in the afternoon can take both 100 mg doses as a single 200 mg dose or as 2 separate doses with a non-standardized meal or snack (once at enrollment and once in the evening); subjects randomized to 400 mg CAMB who enroll in the afternoon can take both 200 mg doses as a single 400 mg dose or as 2 separate doses with a non-standardized meal or snack (once at enrollment and once in the evening).

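### The only named renal analysis is a yes/no creatinine flag, which about 33 women per arm leave insensitive to a general shift; add a baseline-adjusted creatinine difference with a confidence interval beside it

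*Combined protocol and SAP*

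**What the plan says.** The Objectives in the synopsis make safety primary and comparative: "The primary objective of this study is to evaluate the safety of 200 mg (100 mg twice daily [BID]) and 400 mg" doses, set against a single dose of fluconazole.

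Under Study Design and Duration, "Approximately 100 women with moderate to severe VVC will be randomized in a 1:1:1 ratio to 1 of 3 treatment groups". Under Analysis Populations, "The Safety Population will include all ITT subjects who received at least 1 dose of study drug".

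The renal endpoint, under Safety Variables, is binary: "Nephrotoxicity will be defined as a 50% increase in serum creatinine from baseline", or a rise of at least 0.3 mg/dL. The analysis named for it, under Statistical Analyses, is "The proportion subjects with hepatotoxicity, nephrotoxicity, and hypokalemia will be summarized by treatment group".

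The same section says that continuous variables are described in each arm by count, mean, SD, median, minimum and maximum, and that safety analyses draw on the laboratory data and are generally descriptive. Serum chemistry is among the safety assessments. The synopsis names no creatinine change from baseline, baseline adjustment, between-arm difference or confidence interval. Under Sample Size Determination, the sample size is described as empirical.

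**The concern.** A comparative primary objective calls for a comparative estimate. For the kidney, the plan names only a count of women who cross a threshold. If CAMB raised creatinine modestly in most women, few would cross it, and the named table could show similar, near-zero proportions in all three arms. The measurements behind the flag carry more information about that kind of effect, but the plan does not say that they will be turned into a difference between arms with a stated precision.

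At stake is how the main renal result of the trial is read. A table of zeros in arms of this size is weak reassurance, and a reader who wants the CAMB-minus-fluconazole difference would have to construct it.

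**Working it through.** **1. Arm size.** The plan's own figure reproduces: 75 / 0.75 = 100 randomized, and 100 / 3 = 33.3 per arm. The Safety Population is everyone randomized and dosed, so the 75% mITT factor does not shrink it. I use 33 per arm.

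**2. Which limb of the flag governs.** A 50% rise from baseline B equals 0.5 × B, and 0.5 × B ≥ 0.3 when B ≥ 0.6 mg/dL. From 0.6 mg/dL upward, the 0.3 mg/dL limb is the easier one to meet. Below that, the 50% limb is.

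**3. Assumptions.** The documents give no creatinine SD and no expected effect. I assume a general shift δ of +0.10 mg/dL (varied in step 6), an SD σ of individual change of 0.08 mg/dL (range 0.06 to 0.10), normal changes, one post-baseline value per woman and baselines of at least 0.6 mg/dL.

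**4. The flag.** p = 1 − Φ((0.30 − δ)/σ), and P(at least one in 33) = 1 − (1 − p)^33.

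**5. The mean difference from the same samples.** 95% half-width = 1.96 × σ × √(2/33), before baseline adjustment.

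| σ (mg/dL) | 0.06 | 0.08 | 0.10 |
|---|---|---|---|
| p, one woman flagged | 0.04% | 0.6% | 2.3% |
| P(at least one in a CAMB arm) | 1% | 19% | 53% |
| Half-width (mg/dL) | 0.029 | 0.039 | 0.048 |

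**6. Smaller shifts.** As a measure of information only, power = Φ(δ/(σ√(2/33)) − 1.96), two-sided 5%:

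| δ (mg/dL) | σ = 0.06 | σ = 0.08 | σ = 0.10 |
|---|---|---|---|
| 0.10 | >99% | >99% | 98% |
| 0.05 | 92% | 72% | 53% |
| 0.03 | 53% | 33% | 23% |

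**7. Both limbs of the rule, by simulation.** Assumed: mean creatinine 0.75 mg/dL, between-woman SD 0.12, within-woman SD 0.05 to 0.11, 33 v 33, 4,000 trials. Change SD is √2 × within-woman SD, so 0.07 to 0.16. For a shift of 0.10 mg/dL:

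| Within-woman SD | Flag rate, CAMB v fluconazole | At least one flag in a CAMB arm | Fisher power on the flag | ANCOVA power |
|---|---|---|---|---|
| 0.05 | 0.7% v 0.04% | about 20% | 0% | >99% |
| 0.07 | 3.6% v 0.45% | about 70% | 0.1% | 99% |
| 0.09 | 7.8% v 1.8% | over 90% | 2% | 93% |
| 0.11 | 12.5% v 4.4% | about 99% | 7% | 83% |

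Some baselines now fall below 0.6 mg/dL, so flags are more frequent than in step 4 at a similar change SD. With noisier creatinine a flagged woman becomes likely, but fluconazole women are flagged too and the contrast stays weak. ANCOVA power falls to 31% to 83% at a shift of 0.05 (Fisher below 1%) and to 14% to 42% at 0.03.

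**8. What a table of zeros would mean.** With 0 of 33, the upper two-sided 95% limit is 1 − 0.025^(1/33) = 10.6%. Against 0 of 33 on fluconazole, 5 of 33 gives Fisher p = 0.053 and 6 of 33 gives p = 0.024.

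**9. Harm confined to a few women.** If only some CAMB women rise by 0.4 mg/dL (within-woman SD 0.07), the ranking reverses:

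| Share affected | ANCOVA power | At least one flag in the arm |
|---|---|---|
| 3% | 7% | 62% |
| 10% | 22% | 94% |
| 20% | 59% | >99% |

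**The case against.** The strongest reply is that the signal is not lost. Creatinine is part of serum chemistry, so on a plain reading its values will be summarized by arm. If the same women contribute at both times, the mean change is the post-treatment mean minus the baseline mean, and a +0.10 mg/dL shift would be visible in those tables. This stands. A reader might infer that the plan throws the creatinine values away, and the documents do not support that. What is missing is the between-arm difference, its precision and the baseline adjustment.

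Second, no safety test is planned. The trial is a proof-of-concept study with an empirical sample size and descriptive safety reporting. A reader might infer from the power figures that a planned comparison is underpowered, but there is none. The figures show only how much information each summary carries.

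Third, the 1% to 53% is for one CAMB arm, one post-baseline draw and baselines of at least 0.6 mg/dL. With the same effect in both CAMB arms (66 women), the chance of at least one flag is 34% (3% to 78%). Repeated draws and low baselines raise it further. Any flag rate above 1 − 0.5^(1/33) = 2.1% makes a case in an arm of 33 more likely than not. This also stands: the flag is insensitive to general shifts below its threshold, not to renal harm of every kind.

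Last, the text available is a synopsis. Its silence on change-from-baseline tables is limited evidence that none are intended, but it remains the only specification in the documents.

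**Conclusion.** The point holds in a conditional form. For a comparative primary objective, the only named renal analysis is a flag proportion, with no between-arm estimate or interval. If CAMB shifted creatinine generally by about 0.05 to 0.10 mg/dL, a continuous comparison of the same samples would be much more informative. At +0.10 mg/dL, simulated ANCOVA power is 83% to over 99%, against 0% to 7% for a Fisher test of the flag. All SDs, baselines and shifts here are assumptions.

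A reader might go further and conclude that the continuous analysis cannot miss a renal effect, or that it should replace the flag. Neither follows. It has low power for shifts near 0.03 mg/dL and for large rises in a few women, and the flag is the better display of the latter. The two are complementary. This is a worthwhile, inexpensive improvement; the existing endpoint is not wrong.

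**What to change.** Keep the nephrotoxicity proportion as defined. Add to the SAP, for serum creatinine at each scheduled post-baseline laboratory visit in the Safety Population:

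- change from baseline analysed by ANCOVA with treatment arm and baseline creatinine in the model;
- the adjusted difference for each CAMB dose minus fluconazole, with a 95% CI;
- a label saying that these estimates are descriptive, with no hypothesis test;
- a statement of which value is baseline and which visits enter the analysis.

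The same model for log ALT and log AST is optional; no calculation here bears on it.

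The cost is SAP wording and one model per analyte, with no new samples or visits. The downside is a few more descriptive safety estimates to interpret, some of which will differ from zero by chance.
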